Metformin for Ectopic Fat Deposition and Metabolic Markers in Polycystic Ovary Syndrome (PCOS)

NCT02500147

April 23, 2018

Title: Body composition and metabolic manifestations of insulin resistance in adolescents with polycystic ovary syndrome. Ectopic fat deposition and metabolic markers: Intervention and follow-up portion

Principal Investigator: [name], MS

Study Purpose and Rationale:

Polycystic ovary syndrome (PCOS) affects about 7% of females of reproductive age worldwide and is associated with development of lifelong morbidities including type 2 diabetes mellitus and cardiovascular disease. It commonly first presents in adolescence and young adulthood, which places a significant proportion of this young population at risk for long-term morbidity. Although the underlying etiology of PCOS has not been fully elucidated, insulin resistance (IR) is suggested to be an important underlying causal factor. The association between PCOS and IR further links it to other IR-related disorders including obesity, the metabolic syndrome (MeS) and non-alcoholic fatty liver disease (NAFLD). This constellation of disorders is associated with dyslipidemia, cardiovascular disease and type 2 diabetes mellitus. Recently, NAFLD has been reported to be more prevalent in young individuals with PCOS compared to the general population. Additionally, the progression of hepatic steatosis to non-alcoholic steatohepatitis (NASH) is described to be substantially more rapid in PCOS than in unaffected individuals. Metformin is an insulin sensitizing medication typically used to treat type 2 diabetes mellitus, but also has beneficial effects on IR related conditions such as PCOS and NAFLD; however, its effects on NAFLD in PCOS in the adolescent and young adult populations have not been adequately studied. If, in fact, metformin reduces liver fat in adolescents and young adults with PCOS, their long-term risk of metabolic and cardiovascular disease could be diminished. Additionally, this finding would have both personal and far-reaching beneficial public health benefits. There are limited data that suggest that metformin may also have beneficial effects on bone. If our pilot study demonstrates changes in bone formation markers that corroborate recent proposed mechanisms of action, they could provide proof of concept to support further investigation of the skeletal effects of metformin in a larger randomized clinical trial.

This study proposes to explore the efficacy of metformin to reduce liver fat using novel and minimally invasive imaging and biomarkers in a pilot randomized double-blind placebo-controlled trial.

Study Design:

Eligibility Criteria: PCOS subjects who participated in a previous baseline study and have liver fat greater than or equal to 4.8% by MRS or evidence of insulin resistance (on an oral glucose tolerance test) will be invited to participate in this study with the goal of recruiting 44 subjects who are 13 to 25 years at least two years post-menarche. Oligomenorrheic subjects will complete the protocol during the early follicular phase of the menstrual cycle (days one through seven) and amenorrheic subjects will complete the protocol on any day. **Exclusion criteria:** 1. Presence or history of a medical disorder (e.g. non-classical CAH) or medication known to affect body composition, insulin secretion and sensitivity, or the GH-IGF1 axis (i.e. use of glucocorticoids or thyroid hormone), excessive alcohol use, liver disease (other than NAFLD) indwelling hardware, current or past pregnancy and use of metformin or hormonal contraception within 3 months of enrolling in the previous study.

The protocol will comprise:

- a) Randomization: Subjects whose liver fat is 4.8% or greater or have evidence of insulin resistance on an oral glucose tolerance test (n=22) will be randomized to placebo or extended-release metformin (XR) (500 mg (1 tablet) once a day for one week and then 1000 mg (2 tablets) daily for six months). Randomization will be double-blind and will be performed by randomly selected permuted size 2 and size 4 blocks determined by the CUMC Research Pharmacy with the guidance of a statistician and will be stratified based on presence or absence of insulin resistance.
- b) Intervention: All subjects will receive identically appearing pill bottles labeled "Study Medication" containing their first three-month supply of either metformin XR or placebo. Subjects will be instructed to take pills after dinner and to take one pill once a day for one week and subsequently two pills once a day for the remainder of the first three months. Subjects will be asked to call with any side effects that they may experience. They will be given a pill diary so that they can keep track of their compliance. They will be instructed to call our office if they experience any adverse effects and will be asked to bring their empty pill bottles to their interim visit to further ensure compliance.
- c) Brief interim evaluation: After three months of the intervention phase, subjects will be seen for a general health assessment, which includes weight, blood pressure and a physical examination, and will receive their second three-month supply of their assigned intervention along with a second pill diary. They will again be instructed to call our office if they experience any adverse effects and will be asked to bring their empty pill bottles to their follow-up study visit to further ensure compliance.
- d) Follow-up exam: At the end of six months, subjects will undergo laboratory and body composition testing similar to those performed in the baseline testing. Studies that are not repeated in this protocol are transabdominal pelvic ultrasound, MRI of the ovaries and DXA of the hip, spine and wrist
 - 1) History and physical exam: Height, weight, BMI (percentile and z-score for <20 years), blood pressure, physical exam, Ferriman-Gallwey hirsutism scoring, smoking, alcohol and family history;
 - 2) Laboratory evaluation will be between 0800 and 1000 after an overnight fast via an intravenous catheter for:
 - a) General endocrine panel: Thyroid function, prolactin, 17-hydroxyprogesterone;
 - b) PCOS panel: LH, FSH, estradiol, sex hormone binding globulin, testosterone, free testosterone, androstenedione, dehydroepiandrosterone sulfate (DHEAS);
 - c) Liver panel: Liver enzymes (ALT, AST, GGT), apoptosis markers (Fas, cytokeratin-18 fragments, M30), pancreatic polypeptide, irisin

- d) Cardiovascular risk panel: Cholesterol, triglycerides, HDL, LDL, free fatty acids, c-reactive protein;
- e) IR evaluation: hemoglobin A1C, glucose, insulin, c-peptide and two-hour oral glucose tolerance test (OGTT) after a 75 g glucose challenge with measurement of glucose and insulin at 30, 60, 90 and 120 minutes. IR will be determined by age- and BMI- specific HOMA-IR cutoffs based on a National Health and Nutrition Examination Survey (NHANES) study of 1,164 nonobese adolescents 12 to 19 years old. Other IR indices that will be evaluated are whole body insulin sensitivity index (WBISI) and insulin area under the curve (iAUC);
- f) Bone evaluation: 25-hydroxyvitamin D, 1,25-dihydroxyvitamin D, osteocalcin, c-telopeptide, PTH, P1NP

3) MRS of the liver for intrahepatic lipid content (IHL) and of the right soleus muscle for intramyocellular lipid (IMCL) acquired using standard point resolved spectroscopy sequence (PRESS). Percentage liver fat will be calculated.

4) Total body MRI with 10 mm slices and 40 mm interslice gaps for total body adipose tissue , subcutaneous adipose tissue (SAT) and visceral adipose tissue(VAT);

5) MRI for percentage liver fat.

e) Dual-energy x-ray absorptiometry (DXA): Total body DXA will be performed for total body lean and fat mass, percentage body fat and bone mineral density (BMD).

Statistical Procedures:

Statistical Analysis:

1. Change in liver fat is defined as percentage liver fat at six months minus percentage liver fat at baseline. The difference in mean change between metformin XR and placebo groups as well as its 95% confidence intervals will be calculated. The two-sample t-test will be used to compare groups. Sample Size and Power Calculations: Over a 1.5 year recruitment period, 44 subjects is a feasible recruitable sample size. We generally see at least 100 PCOS patients within our division per year. We also work closely with physicians in the Division of Adolescent Medicine and the Department of Obstetrics and Gynecology who will also serve as sources of study subjects for us. Forty-four subjects randomized 1:1 to metformin versus placebo provided greater than 80% power to detect a 1.4 standard deviation difference in the group average change from baseline to endpoint assuming a 5% type I error rate and an independent T-test. Preliminary data showing subjects with PCOS have an average of 4.8% liver fat, and assuming the average within subject change is less than 0.5+0.5% in the placebo group, the power calculations indicate the minimum detectable difference attributable to metformin treatment to be a 0.7% absolute, or a 15% relative decline in percentage liver fat. After the intent-to-treat analysis we will analyze the influence of partial compliance by adding cumulative dose exposure in to a multiple regression

model assessment of the group difference. Subjects will be stratified based on presence or absence of insulin resistance.

2. The association of percent liver fat with IR, dyslipidemia, VAT, total body adipose tissue, and markers of NAFLD and NASH will be estimated with correlation/regression and change in IR, dyslipidemia, and markers of NAFLD and NASH with change in percent liver fat following metformin with multiple regression. Sample Size and Power Calculations: 44 subjects provide 80% power and 5% alpha to detect a baseline association of liver fat with continuous measures of liver fat markers with r -values $> + 0.46$ when tested against H_0 of $r = + 0.10$. 20 subjects in the longitudinal study provides 80% power and 5% alpha to detect an incremental increase of 0.60 in model R^2 when percentage liver fat is added to treatment assignment to predict change in markers.

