Pregnancy: Study subjects may begin ovulating or menstruating during the study as a response to metformin or naturally. Even if the study subject is not getting her period regularly or at all she will be instructed to always use a birth control method if she is sexually active. She cannot take a birth control pill if she is participating in this study so she should use a barrier method of birth control if she is sexually active. It is important to note that metformin is a category B drug in pregnancy, which means that its effects on a fetus are not fully known. Study subjects are instructed to call the study team as soon as possible if they think they may have become pregnant during the study.

Adverse events:

A serious adverse event associated with metformin use is lactic acidosis; however, this most commonly occurs in patients with congestive heart failure, renal failure and liver failure. We will be screening patients by questionnaire and with laboratory data in order to exclude those with underlying medical conditions. We will instruct patients to call immediately if they develop unexplained hyperventilation, myalgia. Malaise, unusual somnolence or other nonspecific symptoms.

We will be tracking the follow adverse event data at the 3 month and 6 month visits based on known common adverse events associated with metformin use: diarrhea, abdominal pain, nausea/vomiting, gas/bloating and any other side effect the subject may experience.

Potential Benefits:

Families and subjects will be provided with detailed analysis of body composition, OGTT and cardiovascular risk factor results and will be counseled about the implications for future metabolic complications, as well as on how to improve health through diet and exercise. All results will be provided to each subject's primary care physician and/or pediatric endocrinologist if directed by the subject's parents at time of study or later date.

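### Baseline liver fat appears to come from the previous study, with no stated limit on its age and no adjustment for the untreated interval before the first dose

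*Combined protocol and SAP*

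**What the plan says.** The title calls this document the "Ectopic fat deposition and metabolic markers: Intervention and follow-up portion" of a larger project. Under Eligibility Criteria, the candidates are "PCOS subjects who participated in a previous baseline study and have liver fat greater than or equal to 4.8% by MRS", or those with insulin resistance on an OGTT.

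The Study Design section then lists randomization, intervention, an interim visit at three months (weight, blood pressure, physical examination) and a follow-up exam. Liver MRS, liver MRI and the OGTT appear only under the follow-up exam: "At the end of six months, subjects will undergo laboratory and body composition testing similar to those performed in the baseline testing". The next sentence reads: "Studies that are not repeated in this protocol are transabdominal pelvic ultrasound, MRI of the ovaries and DXA of the hip, spine and wrist".

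Item 1 of Statistical Analysis defines the primary outcome: "Change in liver fat is defined as percentage liver fat at six months minus percentage liver fat at baseline". The arms are compared with a two-sample t-test. Baseline is not defined further.

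The eligibility text gives one time window, three months for metformin or hormonal contraception. It is counted back from enrolment in the previous study, not from randomization.

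**The concern.** The outcome is presented as a six-month change. If the value subtracted was measured in an earlier study, each subject's change covers six treated months plus an untreated interval of her own. The plan neither limits that interval nor asks for it to be recorded. Three things are at stake:

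- **Precision.** Real movement in liver fat between the earlier scan and the first dose enters the change score as noise. In a trial of this size the interval may also differ between arms by chance, and no adjustment is planned.
- **Current status.** The value that qualifies a subject, and the insulin-resistance status used for stratification, may no longer hold when she is randomized.
- **Pilot estimates.** Within-arm changes cannot be read as six-month changes. Item 3 offers rates of change in bone measures for the design of future studies. If their baselines also come from the earlier battery, those rates need a known time span too.

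**Working it through.** **Which baseline is meant?** Three parts of the text point to the previous study. The title limits this document to intervention and follow-up. Eligibility rests on that study's results. The follow-up exam is described by reference to a baseline battery, some of which this protocol does not repeat. No step at or before randomization lists liver MRS, liver MRI or an OGTT. This is a strong inference, because no sentence dates the baseline.

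**Inputs.** From item 1: 44 subjects randomized 1:1 (22 per arm), 5% type I error, a 1.4 SD difference, 0.7 points absolute, average liver fat 4.8%, and a placebo change printed as 0.5+0.5%. The last is read as mean 0.5 with SD 0.5. The Randomization paragraph gives n=22. If that is the total, there are 11 per arm. A two-sided test is assumed.

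**The plan's own figures.** 0.7/0.5 = 1.4 SD and 0.7/4.8 = 14.6%, which agree with the stated 1.4 SD and 15%. The noncentral t power for 1.4 SD is 99.5% at 22 per arm, so the stated power above 80% is true with a wide margin. At 11 per arm it is 87.7%.

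**Effect of an older baseline.** The documents give neither the length of the gap nor its variance, so this is a range under assumptions. Let the SD of 0.5 belong to a six-month span, let m be the baseline's age in months at first dose (the same for all subjects), and let f be the share of variance that accumulates with time:

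SD = √[0.25(1 − f) + 0.25 f (6 + m)/6]

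- f = 1, m = 6: √0.50 = 0.707; m = 12: √0.75 = 0.866
- f = 0.5, m = 6: √(0.125 + 0.25) = 0.612; m = 12: √(0.125 + 0.375) = 0.707

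The 95% CI half-width at 22 per arm is 2.018 × SD × √(2/22). Power is for a 0.7-point difference.

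| Baseline age | Share f | SD | Half-width, 22/arm | Power, 22/arm | Power, 11/arm |
|---|---|---|---|---|---|
| 0 months | any | 0.500 | 0.30 | 99.5% | 88% |
| 6 months | 1 | 0.707 | 0.43 | 89% | 60% |
| 12 months | 1 | 0.866 | 0.53 | 75% | 44% |
| 6 months | 0.5 | 0.612 | 0.37 | 96% | 72% |
| 12 months | 0.5 | 0.707 | 0.43 | 89% | 60% |

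At 22 per arm, power is 80% when 0.7/SD = 0.8646, that is SD = 0.810 and variance 0.655. With f = 1 this is reached at m = 6 × (0.655/0.25 − 1), about 9.7 months. With f = 0.5 it is about twice that, 19.5 months.

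**Bias check.** 20,000 trials were simulated with 22 per arm, gaps uniform on 0 to 18 months in both arms, a mean drift of 0.5 points per six months and no treatment effect. The t-test rejected in 5.1%, and the mean difference between arms was about −0.001 points.

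**The case against.** The baseline portion has its own procedures, which are not in these documents, and a rule on timing may be there. The text also fits a short hand-off: item 1 describes recruitment from current clinic patients over 1.5 years, and a drug window counted from the earlier enrolment makes most sense if that enrolment is recent. This stands. Baselines that are months or years old are permitted by the text but not shown by it.

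The power loss depends on how much of the SD accumulates. Measurement error and reversible fluctuation do not grow with time, and item 1 attaches no time span to its placebo figure. This also stands, and is why two values of f are shown. The figures for 11 per arm rest on a separate inconsistency over the number randomized.

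Some stronger inferences are tempting, but the documents do not support them:

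- **That the arms are compared with bias.** Randomization comes after the earlier scan, so the untreated interval is balanced in expectation.
- **That a six-month rate is overstated two- or three-fold.** This needs one constant rate across untreated and treated time. A metformin effect can arise only during treatment, and a rise before treatment would make a later fall look smaller.
- **That no laboratory values are taken at entry.** The Metformin paragraph under Protection Against Risk and the Adverse events section describe screening by history or questionnaire and blood tests, including liver and kidney function. What is missing at randomization is liver fat and the OGTT.
- **That the documents show drift before treatment.** The rationale's remark on faster progression concerns steatosis becoming NASH, not liver-fat percentage. The diet and exercise counselling under Potential Benefits is not placed before randomization.

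**Conclusion.** The point holds as a gap in the definition of the primary outcome. By strong inference, change is measured from a previous-study value of unbounded age, and the analysis ignores elapsed time. The between-arm test remains valid. The possible harms are lost precision, outdated qualifying values and strata, and within-arm changes over an unknown span.

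The size cannot be derived from the documents. Under the stated assumptions, a baseline 6 to 12 months old costs between about 4 and 25 points of power at 22 per arm. There the plan's 80% is lost only if baselines are typically older than about 10 to 19 months. At 11 per arm the margin is much smaller: power falls from 88% to between 44% and 72%. If actual gaps are short, the loss is small and the fix mainly documents that. This is an inexpensive improvement and does not challenge the trial's validity.

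**What to change.** 1. In item 1, define baseline as the dated liver-fat measurement from the previous study, if that is what is meant.
2. Record the interval from that measurement to the first dose for every subject, and report its distribution by arm.
3. Replace the unadjusted t-test with a linear model for liver fat that includes treatment, baseline liver fat, the interval and the insulin-resistance stratum.
4. Compute within-arm rates, including those for bone measures in item 3, from actual dates.
5. State the maximum baseline age the sponsor will accept, or cite the baseline protocol's rule if there is one. The length is the sponsor's choice.

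The interval term removes only drift that follows the interval on average. It does not remove individual movement, which only the limit in step 5 contains. Adjusting for baseline liver fat also helps, because an old value then counts only as far as it still predicts the six-month value.

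The cost is one recorded date and one degree of freedom per covariate, three in all (42 to 39 residual degrees of freedom with 44 subjects, 20 to 17 with 22). A limit on age may also exclude a few participants from a pool restricted to the previous study, which is a real trade-off in a pilot of this size.

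### The liver-fat t-test names no covariate although randomization is stratified by insulin resistance; a stratum term would be a cheap gain in precision and calibration, not the repair of an error

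*Combined protocol and SAP*

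**What the plan says.** The outcome is a change score: "Change in liver fat is defined as percentage liver fat at six months minus percentage liver fat at baseline" (Statistical Analysis, item 1). The plan reports the difference in mean change with a 95% confidence interval, and "The two-sample t-test will be used to compare groups". No covariate is named. The only regression planned for the group difference is a later look at partial compliance, which adds cumulative dose.

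Under Study Design, a) Randomization, the allocation uses permuted blocks of 2 and 4 and "will be stratified based on presence or absence of insulin resistance". Item 1 of the Statistical Analysis ends with nearly the same words: "Subjects will be stratified based on presence or absence of insulin resistance".

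The power statement for 44 subjects randomized 1:1 claims "greater than 80% power to detect a 1.4 standard deviation difference", using an independent t-test. The detectable difference is 0.7 percentage points, "assuming the average within subject change is less than 0.5+0.5% in the placebo group". Two smaller counts also appear: "insulin resistance on an oral glucose tolerance test (n=22) will be randomized to placebo" in the randomization paragraph, and "20 subjects in the longitudinal study provides 80% power and 5% alpha" in item 2.

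**The concern.** Stratified blocks force the arms to be nearly balanced on IR. If IR predicts change in liver fat, that balance makes the treatment difference less variable than an unstratified t-test assumes. The t-test leaves the between-stratum variation in its error term, so its interval is wider than needed and its type I error falls below 5%. Part of what the stratification bought is then not used.

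The closing sentence of item 1 does not settle the matter. It may restate the allocation or may intend a stratified analysis, and an analyst could choose between these after seeing data. In a small pilot trial the estimate and its interval are the main product, so both precision and an unambiguous method matter.

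**Working it through.** **Inputs from the documents.** N = 44, 1:1; 22 and 20 are also tried because those counts appear. Detectable difference 0.7 points and 1.4 SD, so the SD of change is 0.7/1.4 = 0.5 points. This agrees with reading the placebo-group assumption as mean 0.5, SD 0.5. Two-sided 5% is assumed, as sidedness is not stated.

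**Not in the documents, so varied.** The difference between IR strata in mean change, the proportion IR-positive, the SD of baseline liver fat, and its correlation with change.

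**1. The plan's own figure.** Noncentral t power at 1.4 SD:

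| N | Power |
|---|---|
| 44 | 99.5% |
| 22 | 87.7% |
| 20 | 84.1% |

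The claim of more than 80% is true at every count.

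**2. Stratum term, closed form.** Let p be the IR-positive share and e the stratum difference in within-stratum SDs. With the strata balanced across arms, the t-test's error variance is inflated by 1 + p(1-p)e². The ratio of interval widths (stratum model to t-test) is about 1/√(1 + p(1-p)e²), before a small degrees-of-freedom cost.
- p = 0.5: e = 1.0 gives 1/√1.25 = 0.894; e = 0.5 gives 1/√1.0625 = 0.970; e = 0.25 gives 1/√1.0156 = 0.992.
- p = 0.9: e = 1.0 gives 1/√1.09 = 0.958; e = 0.5 gives 1/√1.0225 = 0.989.

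The degrees-of-freedom cost, t(N-3)/t(N-2), is 1.0007, 1.0034 and 1.0042 at N = 44, 22 and 20. Incomplete blocks add a little more when one stratum is small.

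**3. Stratum term, simulation.** Permuted blocks of 2 and 4 within IR strata, no treatment effect, N = 44, 22 and 20:

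| IR-positive | Stratum difference | Interval with stratum term |
|---|---|---|
| 50% | 1.0 SD | about 11% narrower |
| 50% | 0.5 SD | 3% narrower |
| 50% | 0.25 SD | under 1% narrower |
| 50% | none | 0.1-0.6% wider |
| 90% | 1.0 SD | 3-4% narrower |
| 90% | 0.5 SD | 0-1% narrower |
| 90% | none | 0.2-1.1% wider |

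At a 50% split and 1.0 SD the t-test's type I error is about 2-4%, while the stratum model stays near 5%. The closed form agrees: at N = 44 the effective critical value is 2.018/0.894 = 2.26, a two-sided error of about 2.9%. The average error of the unadjusted estimate was within 0.007 SD of zero, so there is no bias.

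**4. In liver-fat points at N = 44.** The plan's 0.5 is the total SD of change.
- t-test half-width: 2.018 × 0.5 × √(4/44) = 0.30.
- If the strata split evenly and differ by 0.5 points, the between-stratum variance is 0.25² = 0.0625 and the within-stratum variance is 0.25 - 0.0625 = 0.1875. The half-width becomes 2.020 × √0.1875 × √(4/44) = 0.26.

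That is about 13% narrower. It exceeds 11% because 0.5 points is 0.5/√0.1875 = 1.15 within-stratum SDs.

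**5. Stratum and baseline terms together, no IR effect.** Assume equal variances at baseline and six months. Their correlation is then ρ = 1 - 0.125/SDb², where SDb is the baseline SD. The width ratio to the t-test is √[(1+ρ)/2 × (N-3)/(N-4)] × t(N-4)/t(N-2).

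| Assumed SDb (points) | ρ | N=44 | N=22 | N=20 |
|---|---|---|---|---|
| 0.5 | 0.50 | 0.878 | 0.896 | 0.901 |
| 1 | 0.875 | 0.982 | 1.002 | 1.007 |
| 2 | 0.969 | 1.006 | 1.027 | 1.032 |
| 3 | 0.986 | 1.010 | 1.031 | 1.037 |

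The range runs from 12% narrower to about 4% wider. A clear gain appears only at the smallest assumed SD, unless change depends on baseline more strongly than equal variances imply.

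**The case against.** The closing sentence of item 1 stands in the analysis section, directly after a regression for the group difference, and the allocation strata had already been described. It can fairly be read as an intended stratified analysis. A reader might infer that the plan definitely leaves IR out; the text does not support that. What it shows is a sentence that names no method beside a t-test that names no covariate. This objection stands and limits the point to an ambiguity plus a missing specification.

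The 11% figure needs the strata to differ by a full SD of change, which is large beside the plan's 1.4 SD treatment target, and nothing in the documents supports that size. Entry is through liver fat or IR, so the IR-negative stratum could be small, which shrinks the gain further. This also stands, and is why the smaller differences and the 90% split are shown.

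Finally, the test agrees with its own power calculation, power at the target effect is high, and any miscalibration is conservative. That removes any claim of invalidity. It does not remove the case for the change, because high power at 1.4 SD says little about smaller effects, and the promised interval can be narrower at almost no cost.

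**Conclusion.** The point holds as a recommended improvement. The planned t-test is valid. A reader might infer from the mismatch with the randomization that the comparison is biased or that false positives are inflated. Neither follows: randomization protects the estimate, and ignoring a prognostic stratum pushes the type I error below 5%, not above it.

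The possible gain from the stratum term runs from nothing to about 11% in interval width (13% in the worked example in liver-fat points). It depends on an IR effect and an IR split that the documents do not give. With no IR effect the loss is at most about 1%.

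A reader might also expect baseline adjustment to help as a matter of course. The figures do not show that here: without a baseline SD or a correlation with change, the two terms together could narrow the interval by 12% or widen it by about 4%. The stratum term is therefore the main recommendation and the baseline term secondary. The differing counts of 44, 22 and 20 are a separate matter and do not change this conclusion.

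**What to change.** In Statistical Analysis item 1, make the main analysis a linear model of change in percentage liver fat on treatment and IR stratum, with baseline percentage liver fat as a prespecified additional covariate. Report the adjusted difference with its 95% confidence interval and keep the two-sample t-test as a sensitivity analysis. Reword the closing sentence of item 1 to say this.

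Two details need stating:
- The IR term is the grouping used at randomization, not a status re-derived at follow-up. The randomization paragraph refers to the glucose tolerance test, while the follow-up IR evaluation uses HOMA-IR cutoffs.
- Baseline liver fat comes from the same imaging method as the outcome, since the follow-up exam lists both MRS and MRI.

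The cost is SAP wording, using data the trial already collects. The stratum takes one degree of freedom and baseline a second, leaving 40 of 42 at N = 44, 18 of 20 at N = 22, or 16 of 18 at N = 20. At worst in the ranges shown, the interval is about 1% wider with the stratum alone, or 4% wider with both terms at N = 20.

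### The stated minimum detectable difference of 0.7 points (15%) is about 1.6 times the correct value for 44 subjects, and the number randomized is given as both 22 and 44

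*Combined protocol and SAP*

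**What the plan says.** Statistical Analysis, item 1, states: "Forty-four subjects randomized 1:1 to metformin versus placebo provided greater than 80% power to detect a 1.4 standard deviation difference" in mean change, at a 5% type I error rate with an independent t-test. It takes average liver fat as 4.8%, "assuming the average within subject change is less than 0.5+0.5% in the placebo group", and concludes that the "power calculations indicate the minimum detectable difference attributable to metformin treatment to be a 0.7% absolute, or a 15% relative decline". It supports the number 44 on recruitment grounds: "44 subjects is a feasible recruitable sample size".

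The numbers of subjects given elsewhere are:

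- Study Design, Eligibility Criteria: "with the goal of recruiting 44 subjects".
- Study Design, a) Randomization: subjects with raised liver fat or "evidence of insulin resistance on an oral glucose tolerance test (n=22) will be randomized to placebo" or metformin.
- Statistical Analysis, item 2: "44 subjects provide 80% power and 5% alpha to detect a baseline association of liver fat", and then "20 subjects in the longitudinal study provides 80% power and 5% alpha" for the analysis of change in markers.

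**The concern.** A minimum detectable difference is the smallest effect that a given sample detects at the stated power. For 22 per arm, 1.4 SD is a very large effect, and the power there should be far above 80%. A reader who takes the sentence at face value will think that effects between about 0.43 and 0.7 points are out of the trial's reach. On the plan's own SD, 44 subjects have 80% power or more across that range. This matters for a pilot whose results may guide later work.

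The reader also cannot tell whether the primary comparison has 11 or 22 subjects per arm, because the Randomization paragraph and item 1 differ by a factor of two unless 22 means per arm. The correct minimum depends on which it is.

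**Working it through.** **Inputs**

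- Item 1: 44 subjects, 1:1, so n = 22 per arm; 5% type I error; independent t-test; power above 80%; effect 1.4 SD; mean liver fat 4.8%.
- SD of change: 0.5 points, reading 0.5+0.5% as mean ± SD. The plan's own figures support this, since 0.7 / 1.4 = 0.5.
- Assumed: a two-sided test (sidedness is not stated), 80% power (the only level named), and the same SD in both arms.

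**The plan's conversion reproduces.** 1.4 × 0.5 = 0.7 points, and 0.7 / 4.8 = 14.6%, which rounds to 15%. The 0.7 points is therefore the 1.4 SD in other units.

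**Power at 1.4 SD.** With n per arm, the t statistic has 2n − 2 degrees of freedom and noncentrality d × √(n/2). For n = 22 and d = 1.4 there are 42 degrees of freedom, the noncentrality is 1.4 × √11 = 4.64, and the two-sided critical value is 2.018. Power is 99.5%. The statement that power exceeds 80% is true, but it does not make 1.4 SD the minimum.

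**Smallest difference with 80% power.** Solve power(d) = 0.80 for d, multiply by 0.5 for points, and divide by 4.8 for the relative size:

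| Total randomized | Per arm | Power at 1.4 SD | 80%-power minimum (SD) | Points | Share of 4.8% |
|---|---|---|---|---|---|
| 44 | 22 | 99.5% | 0.865 | 0.43 | 9.0% |
| 22 | 11 | 87.7% | 1.256 | 0.63 | 13.1% |
| 20 | 10 | 84.1% | 1.325 | 0.66 | 13.8% |
| 18 | 9 | 79.6% | 1.407 | 0.70 | 14.7% |

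For 44 the overstatement is 1.4 / 0.8646 = 1.62. This ratio needs no SD, because the plan gives the effect in SD units.

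**Other assumptions for 44 subjects.** The minimum is 1.00 SD at 90% power, 1.11 SD at 95%, 1.32 SD at 99%, 0.76 SD one-sided at 80%, and 1.07 SD with a 1% type I error at 80%. None reaches 1.4 SD.

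**A different SD.** For 44 subjects, 0.7 points is the 80% minimum only if the SD is 0.7 / 0.8646 = 0.81. Then 0.7 points is 0.865 SD, not 1.4 SD. No SD makes both stated figures the minimum for 44.

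**Sensitivity of power for 0.7 points to the SD**

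| SD of change | 44 total | 22 total | 20 total |
|---|---|---|---|
| 0.5 | 99.5% | 87.7% | 84.1% |
| 0.6 | 96.6% | 74.0% | 69.4% |
| 0.9 | 71.2% | 41.2% | 37.7% |

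**The number randomized.** Eligibility Criteria and Randomization use the same entry condition (liver fat of at least 4.8% or insulin resistance), so no further selection step explains a drop from 44 to 22. As written, the 22 covers both treatments together. The 1.4 SD figure fits a total of about 18 to 20, which may mean that it was carried over from a smaller design; the documents do not show this.

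**The case against.** The strongest reply is that little follows from the error. The power sentence is true, 44 is justified by feasibility and not by the detectable difference, and the study is a pilot. Half of 44 is exactly 22, so n=22 is most naturally a per-arm figure with the label missing; two other statements give 44. Permuted blocks can be generated to any length, so the randomization list need not depend on the total. All of this is fair. It makes the matter a correction to the text and not a design fault, and I do not rest the point on the randomization list. But the per-arm reading is not written, and it would leave the 20 unexplained.

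The factor of 1.62 also depends on 80% power and a two-sided test. It would be 1.40 at 90% power and 1.84 for a one-sided test at 80%. That is right, but the stated figure is too large in every case. The two-sided reading is supported by the planned 95% confidence interval.

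Finally, the SD of 0.5 comes from a possibly garbled expression, is worded as an upper bound and describes the placebo group only. This objection stands for the figures in points. Power for 0.7 points exceeds 80% at totals of 44, 22 and 20 if the SD is 0.5; at an SD of 0.6 that holds only for 44. Any restated power should therefore carry its SD.

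**Conclusion.** The concern holds on both counts. For the stated 44 subjects the minimum detectable difference is 0.865 SD and not 1.4 SD (two-sided 5% t-test, 80% power), so the plan overstates it by a factor of 1.62. With an SD of change of 0.5 in both arms, that is 0.43 points (9% of 4.8%) against the stated 0.7 points (15%). If only 22 are randomized the minimum is 0.63 points (13%), so the stated figure matches neither total. If 44 are randomized the error is conservative, and the trial can detect smaller effects than it claims. The conflict between 22 and 44 may be only a missing label, but as written the number randomized is inconsistent, and the 20 longitudinal subjects are not defined. These calculations make no allowance for dropout, because the documents give none.

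**What to change.** 1. Give one randomized total in Study Design and in Statistical Analysis items 1 and 2. If 22 is per arm, write: 22 per arm, 44 in total.
2. Say what the 20 subjects in the longitudinal analysis represent. If they are expected completers, state the assumed loss and give the primary power on the same basis.
3. Write out the assumed SD of change, the power level and the sidedness of the test.
4. Restate the minimum for the chosen total. For 44: 22 per arm give 80% power (two-sided 5% t-test) to detect 0.87 SD, which is 0.43 points or 9% of 4.8% if the SD of change is 0.5. For 22: 11 per arm give 80% power to detect 1.26 SD, which is 0.63 points or 13% on the same SD.
5. If 0.7 points is meant as a target difference, call it that and give its power with the SD attached: at an SD of 0.5, 99.5% for 44 or 87.7% for 22. Add a short range over other SDs.

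The cost is rewording the two sample-size paragraphs and changing one number or label in the Randomization paragraph. No extra subjects are needed, and the test does not change.
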